### **6.1.1.2 Serious Adverse Events**

If an adverse event meets any of the following criteria, it is to be reported to AbbVie as a SAE within 24 hours of the site being made aware of the SAE.

**Death of Subject**            An event that results in the death of a subject.

Life-Threatening	An event that, in the opinion of the investigator, would have resulted in immediate fatality if medical intervention had not been taken. This does not include an event that would have been fatal if it had occurred in a more severe form.
Hospitalization or Prolongation of Hospitalization	An event that results in an admission to the hospital for any length of time or prolongs the subject's hospital stay. This does not include an emergency room visit or admission to an outpatient facility.
Congenital Anomaly	An anomaly detected at or after birth, or any anomaly that result in fetal loss.
Persistent or Significant Disability/Incapacity	An event that results in a condition that substantially interferes with the activities of daily living of a study subject. Disability is not intended to include experiences of relatively minor medical significance such as headache, nausea, vomiting, diarrhea, influenza, and accidental trauma (e.g., sprained ankle).
Important Medical Event Requiring Medical or Surgical Intervention to Prevent Serious Outcome	An important medical event that may not be immediately life-threatening or result in death or hospitalization, but based on medical judgment may jeopardize the subject and may require medical or surgical intervention to prevent any of the outcomes listed above (i.e., death of subject, life-threatening, hospitalization, prolongation of hospitalization, congenital anomaly, or persistent or significant disability/incapacity). Additionally, any elective or spontaneous abortion or stillbirth is considered an important medical event. Examples of such events include allergic bronchospasm requiring intensive treatment in an emergency room or at home, blood dyscrasias or convulsions that do not result in inpatient hospitalization, or the development of drug dependency or drug abuse.

For SAEs with the outcome of death, the date and cause of death will be recorded on the appropriate case report form.

### **6.1.1.3 Adverse Events of Special Interest**

The following AEs of special interest will be monitored during the study (see detailed toxicity management in Section 6.1.7):

- Serious infections, opportunistic infections, herpes zoster, and TB;
- Malignancy (all types);
- Adjudicated gastrointestinal perforations;
- Adjudicated cardiovascular events (e.g., major adverse cardiovascular event [MACE]);
- Anemia;
- Decreased neutrophil counts;
- Decreased lymphocyte counts;
- Increased serum creatinine and renal dysfunction;
- Hepatic events and increased hepatic transaminases;
- Increased creatine phosphokinase (CPK);
- Adjudicated embolic and thrombotic events (non-cardiac, non-CNS).

### **6.1.2 Adverse Event Severity**

The Investigator will classify adverse events according to the Rheumatology Common Toxicity Criteria v.2.0 ([Appendix R](#)).

### **6.1.3 Relationship to Study Drug**

The Investigator will use the following definitions to assess the relationship of the adverse event to the use of study drug:

Reasonable Possibility	After consideration of factors including timing of the event, biologic plausibility, clinical judgment, and potential alternative causes, there is sufficient evidence (information) to suggest a causal relationship.
No Reasonable Possibility	After consideration of factors including timing of the event, biologic plausibility, clinical judgment, and potential alternative causes, there is insufficient evidence (information) to suggest a causal relationship.

For causality assessments, events assessed as having a reasonable possibility of being related to the study drug will be considered "associated." Events assessed as having no reasonable possibility of being related to study drug will be considered "not associated." In addition, when the Investigator has not reported a causality or deemed it not assessable, AbbVie will consider the event associated.

[figure not shown]
If an investigator's opinion of no reasonable possibility of being related to study drug is given, an Other cause of event must be provided by the investigator for the Serious Adverse Event.

#### **6.1.4 Adverse Event Collection Period**

All AEs reported from the time of study drug administration until 30 days following discontinuation of study drug administration have elapsed will be collected, whether solicited or spontaneously reported by the subject. Subjects who discontinue study drug treatment but continue to participate in the study will have SAEs and nonserious AEs collected for the remainder of study participation. In addition, SAEs and protocol-related nonserious AEs will be collected from the time the subject signed the study-specific informed consent.

Adverse event information will be collected as shown in [Figure 5](#).

**Figure 5. Adverse Event Collection**

Additionally, in order to assist the adjudication process, additional information on any potential cardiovascular events including thromboembolic events will be collected, if applicable.

In case of any of the following reported events, an appropriate supplemental eCRF should be completed:

- Cardiac events;
- Myocardial infarction or unstable angina;
- Heart failure;
- Cerebral vascular accident and transient ischemic attack;
- Cardiovascular procedures (SAE Supplemental Procedure eCRF);
- Embolic and thrombotic events (non-cardiac, non-CNS);
- Hepatic;
- Renal;
- Herpes Zoster Infection;
- CPK increase considered by the investigator to be an AE.
- COVID-19.

Supplemental study case report forms should be completed in the event of COVID-19 related missed/virtual visits, study drug interruptions or discontinuations, or adverse

events (including documentation of specific signs/symptoms of infection and testing results).

COVID-19 infections should be captured as adverse events. If the event meets the criteria for a serious adverse event (SAE), then follow the SAE reporting directions per the protocol and above.

The following COVID-19 related supplemental eCRFs should be completed (for both serious and non-serious events):

- COVID-19 Supplemental Signs/Symptoms
- COVID-19 Status Form

### **6.1.5 Serious Adverse Event Reporting**

In the event of an SAE, whether associated with study drug or not, the Investigator will notify Clinical Pharmacovigilance within 24 hours of the site being made aware of the SAE by entering the SAE data into the electronic data capture (EDC) system (RAVE®). SAEs that occur prior to the site having access to the RAVE system, or if RAVE is not operable, should be documented on the SAE Non-CRF forms and emailed (preferred route) or faxed to Clinical Pharmacovigilance within 24 hours of the site being made aware of the SAE.

Email: [contact]
--

FAX to: [contact]
----------------------------------

For safety concerns, contact the Immunology Safety Team at:

for upadacitinib and/or the Summary of Product Characteristics (SmPC) for MTX, as applicable.

In Japan, the Principal Investigator will provide documentation of all SAEs to the Director of the investigative site and the Sponsor.

#### **6.1.6 Pregnancy**

Pregnancy in a study subject must be reported to AbbVie within 24 hours after the site becomes aware of the pregnancy. Subjects who become pregnant during the study must be discontinued from study drug (Section 5.4.1).

Information regarding a pregnancy occurrence in a study subject and the outcome of the pregnancy will be collected. Pregnancies in study subjects will be collected from the date of the first dose through 180 days following the last dose of study drug.

Pregnancy in a study subject is not considered an AE. However, the medical outcome of an elective or spontaneous abortion, stillbirth, or congenital anomaly is considered an SAE and must be reported to AbbVie within 24 hours of the site becoming aware of the event.

Subjects and partners of subjects receiving MTX should avoid pregnancy throughout the course of the study, starting with the Screening Visit through 180 days after the last study drug administration for female subjects and male subjects receiving MTX. Male subjects receiving MTX should also refrain from donating sperm for up to 180 days post last dose of study drug. Results of a positive pregnancy test or confirmation of a pregnancy will be assessed starting with the Screening Visit through the final study visit.

#### **6.1.7 Toxicity Management**

The toxicity management of the AEs including AEs of special interest consists of safety monitoring (review of AEs on an ongoing basis, and periodical/ad hoc review of safety issues by a safety data monitoring committee), interruption of study drug dosing with appropriate clinical management if applicable, and discontinuation of the subjects from

the study drug. The management of specific AEs and laboratory parameters is described below.

For subjects who discontinued study drug, but continued study participation and are instead on standard of care therapies, these toxicity management requirements do not apply (including alerts from the central lab) and any intolerability to standard of care therapies should be managed by the prescribing physician.

**Serious Infections:** Subjects should be closely monitored for the development of signs and symptoms of infection during and after treatment with study drug. Study drug should be interrupted if a subject develops a serious infection or an opportunistic infection. A subject who develops a new infection during treatment with study drug should undergo prompt diagnostic testing appropriate for an immunocompromised subject. As appropriate, antimicrobial therapy should be initiated, and the subject should be closely monitored. Re-challenge with study drug may occur once the infection has been successfully treated. Subjects who develop active TB must be discontinued from study drug.

**COVID-19:** Interrupt study drug in subjects with a confirmed diagnosis of COVID-19. Consider interrupting study drug in subjects with signs and/or symptoms and suspicion of COVID-19. The COVID-19 eCRF must be completed.

**Herpes zoster:** If a subject develops herpes zoster, consider temporarily interrupting study drug until the episode resolves.

**Gastrointestinal Perforation:** If a diagnosis of gastrointestinal perforation is confirmed (other than appendicitis or penetrating injury), the subject must be permanently discontinued from study drug.

**Cardiovascular Events (MACE):** Subjects presenting with potential cardiovascular events should be carefully monitored. These events will be reviewed and adjudicated by an independent Cardiovascular Adjudication Committee in a blinded manner.

**Thrombosis Events:** Subjects who develop symptoms of thrombosis should be promptly evaluated and treated appropriately. If the diagnosis of deep vein thrombosis, pulmonary embolus or non-cardiac, non-neurologic arterial thrombosis is confirmed, the subject must be discontinued from study drug.

**Malignancy:** Subjects who develop malignancy other than NMSC or carcinoma in situ of the cervix must be discontinued from study drug. Information including histopathological results should be queried for the confirmation of the diagnosis. Periodic skin examination is recommended for subjects who are at increased risk for skin cancer.

**ECG Abnormality:** Subjects must be discontinued from study drug for an ECG change considered clinically significant and with reasonable possibility of relationship to study drug OR a confirmed absolute QTcF value > 500 msec.

**Management of Select Laboratory Abnormalities:** For any given laboratory abnormality, the Investigator should assess the subject, apply the standard of care for medical evaluation and treatment following any local guidelines. Specific toxicity management guidelines for abnormal laboratory values are described in [Table 4](#), and may require an appropriate supplemental eCRF to be completed. All abnormal laboratory tests that are considered clinically significant by the Investigator will be followed to a satisfactory resolution. If a repeat test is required per [Table 4](#), the repeat testing must occur as soon as possible.

**Table 4. Specific Toxicity Management Guidelines for Abnormal Laboratory Values**

Laboratory Parameter	Toxicity Management Guideline
Hemoglobin	
 
• If hemoglobin < 8 g/dL interrupt study drug dosing and confirm by repeat testing with new sample.
 
• If hemoglobin decreases <math>\geq 3.0</math> g/dL from baseline without an alternative etiology, interrupt study dosing and confirm by repeat testing with new sample.
 
• If hemoglobin decreases <math>\geq 3.0</math> g/dL from baseline and an alternative etiology is known, the subject may remain on study drug at the investigator's discretion.
 
• If confirmed, continue to withhold study drug until hemoglobin value returns to normal reference range or its baseline value.
 

Absolute neutrophil count (ANC)	
 
• If confirmed < 1000 cells/<math>\mu</math>L by repeat testing with new sample, interrupt study drug dosing until ANC value returns to normal reference range or its baseline value.
 
• Discontinue study drug if confirmed < 500 cells/<math>\mu</math>L by repeat testing with new sample.
 

Absolute lymphocyte counts (ALC)	
 
• If confirmed < 500 cells/<math>\mu</math>L by repeat testing with new sample, interrupt study drug dosing until ALC returns to normal reference range or its baseline value.
 

Total white blood cell count	
 
• If confirmed < 2000 cells/<math>\mu</math>L by repeat testing with new sample, interrupt study drug dosing until white blood cell count returns to normal reference range or its baseline value.
 

Platelet count	
 
• If confirmed < 50,000 cells/<math>\mu</math>L by repeat testing with new sample, interrupt study drug dosing until platelet count returns to normal reference range or its baseline value.
 

**Table 4. Specific Toxicity Management Guidelines for Abnormal Laboratory Values (Continued)**

Laboratory Parameter	Toxicity Management Guideline
AST or ALT	
 
• Interrupt study drug immediately if confirmed ALT or AST <math>> 3 \times</math> ULN by repeat testing with new sample and either a total bilirubin <math>> 2 \times</math> ULN or an international normalized ratio <math>> 1.5</math>.               
 
○ A separate blood sample for INR testing will be needed to measure INR at the time of repeat testing for ALT or AST. A repeat test of INR is not needed for determination if above toxicity management criteria are met.
 
 
 
• Interrupt study drug immediately if confirmed ALT or AST <math>> 3 \times</math> ULN by repeat testing with new sample along with appearance of fatigue, nausea, vomiting, right upper quadrant pain or tenderness, fever, rash, and/or eosinophilia (<math>> 5\%</math>).
 
• Interrupt study drug immediately if confirmed ALT or AST <math>> 5 \times</math> ULN by repeat testing with new sample for more than 2 weeks.
 
• If ALT or AST <math>> 8 \times</math> ULN, interrupt study drug immediately, confirm by repeat testing with new sample, and contact the TA MD.
 
 
Subjects who meet any of the above criteria should be evaluated for an alternative etiology of the ALT or AST elevation and managed as medically appropriate. If applicable, the alternative etiology should be documented in the eCRF. If ALT or AST values return to the normal reference range or its Baseline value, study drug may be restarted. If restarting study drug, documentation should include reason that rechallenge is expected to be safe. If after clinically appropriate evaluation, no alternative etiology for ALT or AST elevation is found or the ALT or AST elevation has not resolved or is not trending down toward normal, the subject should be discontinued from study drug. For any confirmed ALT or AST elevations <math>> 3</math> ULN, complete supplemental hepatic eCRF.
 
 
• Subjects with HBc Ab+ (irrespective of HBs Ab status) and negative HBV DNA at screening who develop the following should have HBV DNA by PCR testing performed within 1 week:               
 
○ ALT <math>> 5 \times</math> ULN OR
 
○ ALT or AST <math>> 3 \times</math> ULN if an alternative cause is not readily identified
 
○ A separate blood sample for HBV DNA PCR testing will be needed at the time of repeat testing for ALT or AST.
 
 
 
 
A positive result for HBV DNA PCR testing in these subjects will require immediate interruption of study drug and a hepatologist consultation should occur within 1 week for recommendation regarding subsequent treatment.

Serum Creatinine	
 
• If serum creatinine is <math>> 1.5 \times</math> the baseline value and <math>> \text{ULN}</math>, repeat the test for serum creatinine (with subject in an euvolemic state) to confirm the results. If the results of the repeat testing still meet this criterion, then interrupt study drug and re-start study drug once serum creatinine returns to <math>\leq 1.5 \times</math> baseline value and <math>\leq \text{ULN}</math>.
 
• If confirmed serum creatinine <math>\geq 2</math> mg/dL, interrupt study drug and re-start study drug once serum creatinine returns to normal reference range or its baseline value.
 
 
For the above serum creatinine elevation scenarios, complete supplemental renal eCRF.

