11. Systemic use of known strong cytochrome P450 3A (CYP3A) inhibitors or strong CYP3A inducers from Screening through the end of the study (refer to [Table 1](#) for examples of commonly used strong CYP3A inhibitors and inducers).
12. Receipt of any live vaccine within 4 weeks prior to the first dose of study drug, or expected need of live vaccination during study participation including at least 4 weeks after the last dose of study drug.
13. History of any malignancy except for successfully treated NMSC or localized carcinoma in situ of the cervix.
14. History of clinically significant (per Investigator's judgment) drug or alcohol abuse within the last 6 months.
15. History of gastrointestinal perforation (other than appendicitis or penetrating injury), diverticulitis, or significantly increased risk for GI perforation per investigator judgment.
16. Conditions that could interfere with drug absorption including but not limited to short bowel syndrome.
17. Subject has been a previous recipient of an organ transplant.
18. History of clinically significant medical conditions or any other reason that in the opinion of the Investigator would interfere with the subject's participation in this study or would make the subject an unsuitable candidate to receive study drug.
19. Active infection(s) requiring treatment with parenteral anti-infectives within 30 days, or oral anti-infectives within 14 days prior the first dose of study drug.
20. History of an allergic reaction or significant sensitivity to constituents of the study drug(s) (and their excipients) and/or other products in the same class.
21. Laboratory values meeting the following criteria within the Screening period prior to the first dose of study drug:
  - Serum aspartate transaminase (AST)  $> 2 \times$  ULN
  - Serum alanine transaminase (ALT)  $> 2 \times$  ULN

- Estimated glomerular filtration rate (GFR) by simplified 4-variable Modification of Diet in Renal Disease (MDRD) formula  $< 40 \text{ mL/min/1.73 m}^2$
  - Total white blood cell count (WBC)  $< 2,500/\mu\text{L}$
  - Absolute neutrophil count (ANC)  $< 1,500/\mu\text{L}$
  - Platelet count  $< 100,000/\mu\text{L}$
  - Absolute lymphocyte count  $< 800/\mu\text{L}$
  - Hemoglobin  $< 10 \text{ g/dL}$
22. History of any of the following cardiovascular conditions:
- Moderate to severe congestive heart failure (New York Heart Association class III or IV),

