### **Randomization/Drug Assignment**

All Screening laboratory results must be reviewed, signed, and dated by the Principal Investigator or Sub-investigator prior to the Baseline Visit. Subjects will not be enrolled into the study if laboratory or other Screening result abnormalities are deemed clinically significant by the Principal Investigator or Sub-investigator.

Subjects will be eligible for randomization if they continue to meet all of the selection criteria (Section 5.2) at Baseline and are willing to continue in the study.

Subjects will be randomized in a 1:1:1 ratio using interactive response technology (IRT) to treatment Groups 2, 3, and 4, below, except for subjects from Japan, who will be randomized in a 2:1:1:1 ratio to Groups 1, 2, 3, and 4:

- Group 1: Upadacitinib 7.5 mg QD monotherapy (subjects in Japan only; N = 75)
- Group 2: Upadacitinib 15 mg QD monotherapy (N = 300) (includes 37 subjects from Japan)

- Group 3: Upadacitinib 30 mg QD monotherapy (N = 300) (includes 37 subjects from Japan)
- Group 4: MTX monotherapy (N = 300) (includes 37 subjects from Japan)

Randomization will be stratified by geographic region.

See Section 5.5.3 for details.

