**Period 1**

- Upadacitinib/Placebo tablet (daily dosing):
  - Allow study drug interruption  $\leq 14$  consecutive days for AEs and emergency surgery during the first 24 weeks;
  - After Week 24, study drug interruption due to AEs/ surgery is allowed  $\leq 21$  days.
- MTX/Placebo capsules (weekly dosing):
  - Allow study drug interruption  $\leq 2$  consecutive missed doses for AEs and emergency surgery during the first 24 weeks;
  - After Week 24, study drug interruption due to AEs/surgery is allowed  $\leq 3$  consecutive doses.
- If the subject must undergo emergency surgery, the study drug should be interrupted at the time of the surgery.
- Elective surgery during the first 24 weeks is discouraged and needs to be discussed with the AbbVie Therapeutic Area Medical Director. If the subject undergoes elective surgery, the study drugs should be interrupted one week prior to the planned surgery.
- After surgery, allow reintroduction of study drugs once the physician has examined the surgical site and determined that it has healed and there is no sign of infection.

## Period 2

- Upadacitinib/Placebo tablet (daily dosing):
  - Up to 30 consecutive days of oral study drug interruption is allowed. The Investigator will make determination if study drug should be restarted for interruptions > 30 days.
- MTX/Placebo capsules or tablets (weekly dosing):
  - Study drug interruption due to AEs/surgery is allowed for  $\leq 3$  consecutive doses. The Investigator will make determination if study drug should be restarted for interruptions > 30 days.
- If the subject undergoes elective surgery, the study drug should be interrupted 1 week prior to the planned surgery. Allow reintroduction of study drug once the physician has examined the surgical site and determined that it has healed and there is no sign of infection.
- If the subject must undergo emergency surgery, the study drug should be interrupted at the time of surgery. Allow reintroduction of study drug once the physician has examined the surgical site and determined that it has healed and there is no sign of infection.

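### The first serum creatinine rule in Table 4 omits return to baseline as a restart condition, so a subject with baseline above ULN can recover fully and still not qualify to restart

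*Protocol*

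**What the plan says.** The Serum Creatinine row of Table 4 (Protocol Section 6.1.7) has two bullets.

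- **First bullet.** Trigger: creatinine above 1.5 × baseline and above ULN, confirmed on repeat. Then: "If the results of the repeat testing still meet this criterion, then interrupt study drug and re-start study drug once serum creatinine returns to" at most 1.5 × baseline and at most ULN. Both limits must be met.
- **Second bullet.** Trigger: confirmed creatinine of 2 mg/dL or more. Then: "interrupt study drug and re-start study drug once serum creatinine returns to normal reference range or its baseline value".

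The other rows that state a restart value follow the second pattern. For neutrophils the text is "interrupt study drug dosing until ANC value returns to normal reference range or its baseline value". For transaminases it is "If ALT or AST values return to the normal reference range or its Baseline value, study drug may be restarted". The hemoglobin, lymphocyte, white cell and platelet rows do the same.

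Renal eligibility in Exclusion 21 (Section 5.2.2) rests on "Estimated glomerular filtration rate (GFR) by simplified 4-variable Modification of Diet in Renal Disease (MDRD) formula" below 40 mL/min/1.73 m². It sets no limit on creatinine itself. Screening also leaves room for judgement: "Subjects will not be enrolled into the study if laboratory or other Screening result abnormalities are deemed clinically significant" by the investigator (Section 5.3.1.1, Randomization/Drug Assignment).

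**The concern.** The first bullet can ask for a better value than the subject had at enrolment. While creatinine sits at a baseline above ULN, the interruption trigger is not met and the subject takes drug. After an interruption, that same value does not meet the restart condition.

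The strictness also falls unevenly. A subject who rises from 1.40 to 2.05 mg/dL meets only the second bullet and may restart at 1.40. With a ULN of 1.1, a subject who rises from 1.20 to 1.90 meets only the first bullet and may not restart at 1.20. The second subject's relative rise is larger (1.90/1.20 = 1.58 against 2.05/1.40 = 1.46), but the absolute peak is lower, and both have returned fully to baseline.

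At stake are time off drug for a recovered subject and inconsistent handling between sites. Increased serum creatinine is an adverse event of special interest (Section 6.1.1.3), so one clear restart rule is worth having.

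**Working it through.** The plan gives no figure to reproduce. The check compares the two rules directly.

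**Notation.** B = baseline, P = confirmed peak, U = ULN, all in mg/dL. *Normal range* is read as at or below U, and *return to baseline* as at or below B.

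**Inputs from Table 4.** The first bullet triggers if P > 1.5B and P > U, and its restart limit is min(1.5B, U). The second bullet triggers if P ≥ 2.0, and its restart limit is max(U, B).

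**Step 1: only the first bullet applies and B > U.** The condition is 1.5B < P < 2.0, so B < 2.0/1.5 = 1.33. Because B > U, the restart limit is U, which lies below the subject's own baseline. The documents give no creatinine ULN, so a range is shown (steps of 0.01 mg/dL):

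| Assumed ULN | Affected baselines |
|---|---|
| 0.9 | 0.91–1.32 |
| 1.0 | 1.01–1.32 |
| 1.1 | 1.11–1.32 |
| 1.2 | 1.21–1.32 |
| 1.3 | 1.31–1.32 |
| 1.33 or higher | none |

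The peak must lie between 1.5B and 2.0, so the width is 2.0 − 1.5B:

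- B = 1.10: 2.0 − 1.65 = 0.35
- B = 1.20: 2.0 − 1.80 = 0.20
- B = 1.30: 2.0 − 1.95 = 0.05

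**Step 2: only the second bullet applies.** The condition is 2.0 ≤ P ≤ 1.5B, so B ≥ 1.33. Example: B = 1.40 gives 1.5B = 2.10, so P = 2.05 meets only the second bullet. Restart at baseline is allowed and there is no problem.

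**Step 3: both bullets apply.** Compare min(1.5B, U) with max(U, B):

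- B > U: U against B. Example: U = 1.2, B = 1.4, P = 2.2 gives 1.2 against 1.4.
- U/1.5 ≤ B ≤ U: both give U. Example: U = 1.2, B = 1.0, P = 2.1 gives 1.2 under both.
- B < U/1.5: 1.5B against U. Example: U = 1.2, B = 0.7, P = 2.1 gives 1.05 against 1.20.

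No text says which bullet governs when the limits differ.

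**Step 4: can such a subject be enrolled?** This is an illustration, because the MDRD coefficients are assumed and are not in the documents. For a woman aged 60 with creatinine 1.20, eGFR = k × 1.20^−1.154 × 60^−0.203 × 0.742. That gives 45.8 for k = 175 and 48.7 for k = 186, both above 40, so Exclusion 21 does not bar her. A confirmed 1.90 exceeds 1.5 × 1.20 = 1.80 and is below 2.0, so only the first bullet applies. On return to 1.20 she does not qualify to restart if ULN is 1.0 or 1.1. She does qualify if ULN is 1.2 or higher.

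**The case against.** **Restart is not closed off.** A reader might infer that a subject in Step 1 can never restart, or is forced to discontinue. The documents do not support that. Restart is allowed once creatinine reaches ULN. In Period 2, Section 6.1.7 also provides: "The Investigator will make determination if study drug should be restarted for interruptions" longer than 30 days. All subjects had reached the end of Period 1 by September 2018 (Section 5.5.5.2), so Period 2 is what remains. This objection stands: for these subjects the effect falls mainly in the first 30 days of an interruption.

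**The two bullets do not always conflict.** A reader might also infer a clash whenever both triggers are met. Step 3 shows that they agree for any baseline from ULN/1.5 to ULN. Even where they differ, a site can satisfy both by meeting the stricter limit. That is a fair reading, but the protocol does not state it.

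**Discretion.** Table 4 is described as guidelines, and Section 6.1.7 says that "the Investigator should assess the subject, apply the standard of care for medical evaluation and treatment following any local guidelines". That does not say a stated restart value may be set aside. The investigator-restart text in Section 5.5.4 does not help either, because it excludes interruptions for Section 6.1.7 reasons.

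**Deliberate caution.** A stricter renal rule could be intended, given the special-interest status of creatinine. No text says so, and caution does not readily explain requiring a value better than baseline.

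**Rarity.** Several conditions must coincide: a baseline above ULN in a subject not kept out by screening judgement or Exclusion 18, a confirmed rise above 50%, and a peak below 2.0. This stands and limits the size of the point.

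**Conclusion.** The first creatinine bullet is wrong as written, and the point is minor. For a baseline above ULN and below 1.33 mg/dL, with a confirmed peak above 1.5 × baseline and below 2.0 mg/dL, full return to baseline does not satisfy its restart condition. The finding of an omitted option rests on the text alone. Whether anyone can be affected depends on a ULN below 1.33 mg/dL, which the documents do not show. When both triggers are met, the restart limits differ only for a baseline above ULN or below ULN/1.5.

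The number of affected subjects is unknown and probably small. A reader might wonder about the efficacy results. SAP Section 11.1 records that the primary analysis and Period 1 reporting are complete, and nothing here affects them.

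**What to change.** Make two changes to the first creatinine bullet at the next amendment made for other reasons:

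1. After the limits of ≤ 1.5 × baseline and ≤ ULN, add: *or to its baseline value*.
2. Add: *If both criteria are met, the restart condition of the first bullet applies.*

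The first change resolves baselines above ULN, both in Step 1 and when both triggers are met. For B ≤ ULN it changes nothing, since B already meets both existing limits. The second change resolves baselines below ULN/1.5, where 1.5 × baseline would govern (1.05 in the example with ULN 1.2 and baseline 0.7). The interruption triggers stay as they are.

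The cost is one phrase and one sentence, with no added tests. Amendments need ethics approval before implementation (Section 9.1) and the study has about 330 sites, so a stand-alone amendment is not justified. The downside is that a few subjects would restart with creatinine above ULN at their own baseline, which the second bullet already accepts.
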